7.3.1. Reporting Suspected Unexpected Serious Adverse Reactions and Urgent Safety Issues

The Sponsor or designee is responsible for reporting suspected unexpected serious adverse reactions (SUSARs) to regulatory agencies, competent authorities, IRBs/ECs, and investigators

as per local laws and regulations. Fatal and life-threatening SUSARs will be submitted no later than 7 calendar days of the Sponsor's or designee's first knowledge of the event and follow-up information submitted within an additional 8 calendar days, or as otherwise required per local laws and regulations. All other SUSARs will be submitted within 15 calendar days of the Sponsor's or designee's first knowledge of the event. The Investigator is responsible for notifying the local IRBs or ECs of all SAEs that occur at his or her site as required by local regulations or IRB/EC policies, if this responsibility resides with the site.

Investigators are required to report any urgent safety matters to the Sponsor or designee within 24 hours of awareness. The Sponsor or designee will inform regulatory authorities, IRBs/ECs, and investigators, as applicable, of any events (eg, change to the safety profile of inclacumab, major safety findings that may place study participants at risk) that may occur during the clinical trial that do not fall within the definition of a SUSAR but may adversely affect the safety of study participants.

7.4. Reporting Pregnancy

If a participant becomes pregnant during the study the pregnancy must be reported to the Sponsor or designee within 24 hours of awareness. The Investigator will discuss the risks and concerns of study drug exposure to a developing fetus and counsel the participant and/or pregnant partner (or ensure such counselling is provided).

Reported pregnancy of a participant or a participant's partner, while participating in this study, will be monitored for the full duration of the pregnancy and/or followed through a definitive outcome (ie, birth, or spontaneous or elective abortion).

An uncomplicated pregnancy will not be considered an AE or SAE. Pregnancy complications such as spontaneous abortion/miscarriage and congenital anomalies are considered SAEs and must be reported as described in Section 7.3. Note that an elective abortion is not considered an SAE. Pregnancy and pregnancy outcomes must be reported on a Pregnancy Notification Form or Pregnancy Outcome Form, respectively, and sent to the Sponsor or designee within 24 hours of the Investigator site personnel learning of the pregnancy or pregnancy outcome.

The child born to a female participant or partner of a male participant exposed to study drug will be followed for 3 months after delivery. The outcome of any pregnancy and the presence or absence of any congenital abnormality will be recorded in the Pregnancy Outcome Form and reported to the Sponsor or designee. Any congenital abnormalities in the offspring will be reported as an SAE and must be reported as described in Section 7.3.

Information regarding pregnancy testing (including definition of females of childbearing potential) is provided in Section 6.2. Highly effective means of contraception are also listed in Section 6.2.

7.5. Reporting Overdose

If a participant receives more than the protocol-defined dose of study drug and experiences a drug-related AE, this will be reported as an overdose (AEs must be recorded on the AE eCRF) and a protocol deviation. However, if the participant did not experience any AEs, this will only be reported as a protocol deviation.

The Investigator will discuss the risks and concerns of investigational agent exposure with the participant. An overdose with associated AEs must be reported within 24 hours of the Investigator, designee, or site personnel learning of the overdose and reported to the Study Director/Medical Monitor. An overdose must be followed until any adverse effects are resolved or stabilized, or until reasonable attempts to determine resolution of the event are exhausted.

7.6.1. Procedures for Reporting and Documenting VOC Event Data

All VOCs, as defined in Section 5.1, are to be documented within the eCRF within 5 days of a site becoming aware of such event. Each VOC is to be recorded only once on the "Vaso-occlusive Event" eCRF page. All VOCs are to be recorded throughout the entire treatment period, up to Day 91, and should continue until the Follow-Up Visit at Day 161 for participants who do not enroll in the OLE study (or earlier if participant discontinues from the study). The Investigator will classify and provide all the following information for each VOC as follows:

- Diagnosis, which will be limited to one of the five pre-defined VOC events as described in Section 5.1:
 - Uncomplicated VOCs
 - ACS
 - Hepatic sequestration
 - Splenic sequestration
 - Priapism (requiring a visit to a medical facility)

- Onset date,
- Stop date,
- Action taken (None, Required concomitant medication, Temporarily withheld study drug, Permanent discontinuation of study drug, or Other [explain]),
- Whether or not hospitalization or a visit to emergency department, urgent care center, outpatient clinic, or infusion center was required and the duration of the visit,
- Concomitant medications given, and
- Outcome (Recovered without sequelae, Resolved with sequelae, Ongoing, Unknown, Death).

If a participant is hospitalized due to a VOC and during hospitalization develops a non-VOC event that meets the criteria for an SAE, then that event should be reported as a SAE. Any prolongation of a hospitalization due to a non-VOC event (even though they may have initially been hospitalized due to a VOC) is reportable as a SAE in the eCRF.

7.6.2. Source Document Collection for VOC Event Adjudication

For each reported on-study VOC, blinded source documentation to support the reported diagnosis will be submitted by the site to Sponsor, or designee, for review during the VOC adjudication process. Adjudication of VOC events will be performed by a study Adjudication Committee – an independent, blinded panel comprised of experts in SCD. Responsibilities of the Adjudication Committee and definition of VOCs for adjudication will be provided in the Adjudication Committee Charter.

Source documents may include (but are not limited to) the following:

- Clinical notes (including history and PE findings),
- Emergency Department notes (including history and PE findings),
- Hospital discharge summary,
- Clinical laboratory values (eg, hemoglobin concentration values for diagnoses of hepatic or splenic sequestration),
- Physical examination findings,
- Concomitant medications, and
- Chest X-ray (required for reporting an ACS).

7.7. Data Monitoring Committee

In addition to the Sponsor's pharmacovigilance oversight, an independent, unblinded Data Monitoring Committee (DMC) will oversee the safety of participants and overall study conduct for the Phase 3 program, with the support of an independent data coordinating center.

Initial enrollment of study participants will be limited to adults and adolescents 16 years of age or older. The DMC will review all available safety data and PK/PD data (as applicable) from the first 20 participants who have completed a minimum of 90 days of study participation in the

Phase 3 program to make a recommendation about enrollment of participants 12 to 15 years of age. Should the DMC recommend enrollment of participants 12 to 15 years of age, sites will be informed by the Sponsor. The DMC will continue close monitoring by meeting to review data of each 20 participants enrolled 12 to 15 years of age, or every 6 months, whichever occurs first. The DMC may also schedule ad hoc meetings at their discretion or at the Sponsor's request (eg, for a safety signal).

The full description of the DMC structure and responsibilities, as well as details of data to be reviewed and the frequency of the meetings, will be described in the DMC Charter.

7.8. Follow-up of AEs and SAEs

All AEs and SAEs must be followed until resolution, until the condition stabilizes, until the event is otherwise explained, or the participant is lost to follow-up. This includes AEs/SAEs ongoing at completion of the study. The Investigator is responsible to ensure that follow-up includes any supplemental investigations as may be indicated to elucidate as completely as practical the nature and/or causality of the AE or SAE. This may include additional laboratory tests or investigations, histopathological examinations, relevant hospital records (ie, discharge summary), or consultation with other health care professionals. The site must ensure that all participant identifiers are redacted from supportive documentation prior to submission.

The Sponsor, or designee, may request that the Investigator perform or arrange for the conduct of supplemental measurements and/or evaluations. If a participant dies during participation in the study or during a recognized follow-up period, the Sponsor, or designee, should be provided with a copy of any postmortem findings, including histopathology.

New or updated information obtained during SAE follow-up should be recorded on the originally completed SAE form with all changes signed and dated by the Investigator or designee. By signing the SAE form, the Investigator or designee attests to the accuracy and completeness of the data and that he/she has reviewed the report being submitted and approved.

Investigators are not obligated to actively seek SAE information from participants that complete the study, but investigators are encouraged to notify the Sponsor, or designee, of any SAEs of which they become aware occurring at any time after a participant has discontinued or completed the study that they judge may be reasonably related to treatment with study drug or study participation.

7.9. Safety Responsibilities

7.9.1. Investigator

The Investigator's responsibilities include the following:

- Monitor and record all AEs, including SAEs, regardless of the severity or relationship to study drug.
- Determine the seriousness, relationship, and severity of each event.
- Determine the onset and resolution dates of each event.

- Monitor and record all pregnancies and follow up on the outcome of the pregnancy in female participants or the partners of male participants.
- Complete the SAE eCRF within 24 hours of the study site staff becoming aware of the event.
- Complete the AE/SAE and/or AESI eCRF within 24 hours of the study site staff becoming aware of the event.
- Pursue AESI or SAE follow-up information actively and persistently. Follow-up information must be reported to Sponsor, or designee, within 24 hours of the study site staff becoming aware of new information.
- Ensure all AE and SAE reports are supported by documentation in the participants' medical records and submit documentation (with participant identifiers redacted) with SAE reports as required.
- Pursue AE follow-up information, if possible, until the event has resolved or become stable.
- Report SAEs to IRB/IEC, as required by local law.

7.9.2. Sponsor

The Sponsor's responsibilities include the following:

- Safety monitoring/surveillance of AEs and SAEs.
- Before study site activation and participant enrollment, the Medical Monitor, or designee, is responsible for reviewing with study site staff the definitions of AE and SAE, as well as the instructions for monitoring, recording, and reporting AEs and SAEs.
- The Sponsor, or designee, is to notify all appropriate regulatory authorities, central IRBs/ECs, and Investigators of SUSARs, as required by local law, within required time frames.

8. STATISTICAL METHODS

Detailed specifications of the methods for summary and analysis of the data collected in this study will be documented in the statistical analysis plan (SAP).

8.1. Study Endpoints

Study endpoints are provided in Section 3.2.

8.2. Determination of Sample Size

Up to 280 participants will be enrolled in the study. Participants will be randomized in a 1:1 ratio to receive treatment with a single dose of inclacumab or placebo.

The study uses a group sequential design to evaluate the primary efficacy endpoint based on 2 sequential analyses: (i) one interim analysis after a minimum of 75 participants per arm have completed the study through 90 days, and (ii) if required, a final study analysis based on approximately 140 participants per arm.

For the primary endpoint, the planned sample size of up to 280 participants (140 participants per treatment group) provides approximately 90% power to detect a targeted 50% relative reduction in the proportion of participants with at least 1 VOC that required admission to a healthcare facility and treatment with parenteral pain medication within 90 days from a rate of 35% for placebo to 17.5% for inclacumab, using a 2-sided test of the difference in 2 binomial proportions (Normal approximation). To maintain an overall Type I error rate of 0.05, calculations assumed an O'Brien-Fleming boundary of the Lan-DeMets alpha-spending function (East version 6.5). For the sample size calculation, a 5% drop-out rate during the 90-day study period was used.

With this sample size, the smallest observed treatment difference expected to be statistically significant at the final analysis is approximately a 32% relative reduction (ie, reduction in the proportion of participants with at least 1 VOC that required admission to a healthcare facility and treatment with parenteral pain medication within 90 days of randomization from 35% for placebo to 23.8% for inclacumab).

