8.3. Analysis Populations

Two main analysis populations are defined for this study: the intent-to-treat (ITT) population and the safety population.

- The ITT population includes all randomized participants. For analyses based on this
 population, participants will be grouped according to treatment assigned at
 randomization. The ITT population will be the main analysis population for efficacy
 analyses and summaries of demographic and Baseline characteristics.
- The safety population includes randomized participants who received treatment with study drug. For analyses based on this population, participants will be grouped according to the actual treatment received. The safety population will be the main analysis population for safety analyses and summaries of study drug exposure.

Additional analysis populations, such as a per protocol population, will be defined in the SAP, as appropriate.

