8.4.3. Efficacy Analyses

8.4.3.1. Primary Endpoint

For the primary efficacy endpoint, the proportion of participants with at least 1 VOC that required admission to a healthcare facility and treatment with parenteral pain medication within 90 days, will be compared between treatment arms using the exact Cochran-Mantel-Haenszel general association test, stratified by the randomization stratification factors.

Every effort will be made to obtain the 90-day re-admission status for a VOC for each participant. For purposes of the primary analysis, participants with an unknown 90-day re-admission status will be classified as having experienced at least 1 protocol-defined VOC within 90 days (ie, treated as "failure"). Sensitivity analyses evaluating the robustness of results to assumptions regarding drop-outs will be performed, as appropriate.

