2.3. Determination of Sample Size

The original sample size determination was based on statistical power considerations for the primary efficacy endpoint, the proportion of participants with at least 1 VOC that required admission to a healthcare facility and treatment with parenteral pain medication within 90 days of randomization.

As originally planned, the study was to use a group sequential design to evaluate the primary efficacy endpoint based on 2 sequential analyses: (i) one interim analysis after approximately 75 participants per arm have completed the study through 90 days, and (ii) if required, a final study analysis based on approximately 140 participants per arm.

For the primary endpoint, the planned sample size of up to 280 participants (140 participants per treatment group) was to provide approximately 90% power to detect a targeted 50% relative reduction in the proportion of participants with at least 1 VOC that required admission to a healthcare facility and treatment with parenteral pain control within 90 days, from a rate of 35% for placebo to 17.5% for inclacumab, using a 2-sided test of the difference in 2 binomial proportions (Normal approximation). To maintain an overall Type I error rate of 0.05, calculations assumed an O'Brien-Fleming boundary of the Lan-DeMets alpha-spending function (East® version 6.5). For the sample size calculation, a 5% drop-out rate during the 90-day study period was used.

With this original sample size, the smallest observed treatment difference expected to be statistically significant at the final analysis was approximately a 32% relative reduction (i.e., reduction in the proportion of participants with at least 1 VOC that required admission to a healthcare facility and treatment with parenteral pain medication within 90 days from 35% for placebo to 23.8% for inclacumab).

As of June 2023, the Sponsor has decided to discontinue the study prior to full enrollment, with approximately 26% of the total number of planned participants randomized. The ultimate study sample size is based on screening and enrollment at the time of the decision to discontinue, rather than any statistical considerations.

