2.3.1. Basis for Original Sample Size Assumptions

Based on 2016 nationwide re-admission data, a 30-day all cause re-admission rate of 26.9% was reported among patients admitted with a principal diagnosis of sickle cell crisis (Kumar, 2020). The majority (86%) of such re-admissions were due to sickle cell crisis or related diagnosis. Similarly, an analysis of patient claims data (Source Healthcare Analytics Patient Transaction Dataset; August 2017 to July 2018 cohort) showed that among patients with a history of VOC, approximately 50% of patients hospitalized for an index VOC are expected to be re-hospitalized for a VOC within 90 days (data on file). However, overall hospital admissions have decreased with the COVID-19 pandemic (Birkmeyer, 2020) and patients with SCD may try to avoid hospitalizations (McFarling, 2020; Powell, 2020).

In this study, the primary endpoint evaluates, following an index VOC, the occurrence of at least 1 VOC that required admission to a healthcare facility (hospital admission; admission to an emergency room, observation unit, or infusion center for ≥ 12 hours; or 2 visits to an emergency room, observation unit, or infusion center over a 72-hour period) and treatment with parenteral pain medication within 90 days of randomization. For purposes of sample size calculation, it was assumed that approximately 35% of participants in the placebo group experience such a protocol-defined VOC within 90 days of randomization.

The assumption of 5% drop-out rate during the 90-day study period was based on data from the Phase 3 clinical trial of voxelotor, Study GBT440-031, in patients with SCD (data on file).

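### The stated power of about 90% does not allow for drop-outs being counted as failures; if all of the plan's 5% are so counted, it is about 86–87%

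*Protocol*

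**What the plan says.** Protocol section 8.2 states that the planned 140 per arm "provides approximately 90% power to detect a targeted 50% relative reduction" in the proportion with a qualifying VOC within 90 days, from 35% on placebo to 17.5% on inclacumab. The test is a two-sided comparison of two proportions by the Normal approximation. There are two looks with Lan-DeMets O'Brien-Fleming spending and an overall error rate of 0.05. On losses it says only that "a 5% drop-out rate during the 90-day study period was used". The synopsis carries the same text. SAP section 2.3 repeats it in the past tense ("was to provide approximately 90% power to detect a targeted 50% relative reduction"), adding that the final size follows from enrolment at the time of stopping, "rather than any statistical considerations".

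SAP section 2.3.1 gives the meaning of the control rate: "it was assumed that approximately 35% of participants in the placebo group experience such a protocol-defined VOC within 90 days of randomization". It takes the 5% from an earlier Phase 3 trial in sickle cell disease.

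The analysis rules stand elsewhere. Protocol section 8.3: "The ITT population includes all randomized participants". Protocol section 8.4.3.1: "participants with an unknown 90-day re-admission status will be classified as having experienced at least 1 protocol-defined VOC within 90 days", preceded by "Every effort will be made to obtain the 90-day re-admission status for a VOC for each participant". SAP sections 5.3 and 5.3.1 keep both rules. SAP 5.3.1 gives, as its example of unknown status, early discontinuation without a prior readmission.

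**The concern.** The sample-size text and the primary analysis may treat the same participants differently. Inflating a sample for drop-out assumes that those who leave are lost from the denominator and that the event rates are unchanged. The failure rule keeps them in the denominator and gives each an event. Applied equally to both arms, this raises both rates, narrows the difference and increases the variance.

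SAP 2.3.1 defines the 35% by participants who experience a VOC, and neither document says that imputed failures are already included. A reader would take the 90% as covering the specified primary analysis at the plan's own drop-out rate. What is at stake is the accuracy of that description of the design.

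**Working it through.** **Inputs.** Rates 35% and 17.5%, 140 per arm, two-sided 0.05, looks at 75 and 140 per arm (information fraction 75/140 = 0.536) and 5% drop-out, all from Protocol 8.2. All randomized participants are analysed (8.3), and unknown status counts as failure (8.4.3.1).

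**Boundaries.** Lan-DeMets O'Brien-Fleming spending at 0.536 gives critical values 2.849 and 1.972 (one-sided 0.025 spending), or 2.678 and 1.985 (two-sided 0.05 spending). Power comes from the bivariate normal distribution of the two test statistics. Ranges cover both boundary sets and pooled or unpooled variance.

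**Reproducing the stated figure.** The unpooled variance term is 0.35×0.65 + 0.175×0.825 = 0.3719.

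- Drop-outs removed: 140×0.95 = 133 per arm. SE = √(0.3719/133) = 0.0529, and 0.175/0.0529 = 3.31. The final look alone gives Φ(3.31 − 1.972) ≈ 91%. Two-look power is 90.2–91.0%.
- Drop-outs ignored: 140 per arm. SE = √(0.3719/140) = 0.0515, and 0.175/0.0515 = 3.40. The final look alone gives Φ(3.40 − 1.972) ≈ 92%. Two-look power is 91.6–92.3%.

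Either reading supports the stated approximate 90%. In a fixed design, 90% power needs 131 per arm, or 131/0.95 ≈ 138 after inflation, close to the 140 planned.

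**Applying the failure rule.** Let *u* be the share of each arm that drops out with no 90-day status recovered. If drop-out is independent of VOC risk, the analysed rate is

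p′ = u + (1 − u)p.

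The timing of drop-out does not matter, because a participant readmitted before leaving is a failure anyway. With u = 5%:

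- placebo: 0.05 + 0.95×0.35 = 38.25%
- inclacumab: 0.05 + 0.95×0.175 = 21.63%
- difference 16.6 points; relative reduction 1 − 21.63/38.25 = 43.5%

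The variance term is 0.3825×0.6175 + 0.2163×0.7837 = 0.4057. SE = √(0.4057/140) = 0.0538, and 0.16625/0.0538 = 3.09. The final look alone gives Φ(3.09 − 1.972) ≈ 87%. Two-look power is 86.0–86.9%.

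**By share of drop-outs whose status is recovered (140 per arm):**

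| Recovered | u | Two-look power |
|---|---|---|
| all | 0% | 91.6–92.3% |
| three quarters | 1.25% | 90.3–91.1% |
| half | 2.5% | 88.9–89.7% |
| one quarter | 3.75% | 87.5–88.3% |
| none | 5% | 86.0–86.9% |

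A simulation with binomial draws (400,000 trials, pooled z test at both looks) gave 91.9–92.0%, 89.2–89.3% and 86.1–86.4% at u = 0, 2.5% and 5%.

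**Sensitivity to independence.** If drop-outs carry *r* times the average VOC risk, p′ = p + u(1 − rp). At u = 5%, r = 0.5 gives 87.3–88.2% and r = 2 gives 83.0–84.0%. These values of r are assumptions; the documents give none.

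**The case against.** The strongest reply is that no printed figure is wrong. The power is given as approximate and reproduces on its own inputs. A reader might infer that the calculation contains an arithmetic error. The documents do not support that: what is missing is a statement of how the 5% was used.

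A reader might also infer that the claim fails once unknown status passes about 2%, since the computed power crosses 90% at 1.5–2.3%. That treats an approximate figure as a hard line. At 2.5% the power is still about 89–90%, and with a two-point tolerance (88%) the claim lasts to roughly 3.4–4.2%. Only when nearly all drop-outs stay unrecovered is the gap 3 to 4 points.

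Nor is 5% drop-out the same as 5% unknown status. The failure rule concerns status, the plan promises every effort to obtain it, and a participant readmitted before leaving has known status. If drop-outs and events were spread evenly over the 90 days (an assumption), 5% drop-out would leave about 0.05×(1 − 0.35/2) = 4.1% unknown on placebo and 0.05×(1 − 0.175/2) = 4.6% on inclacumab. This stands, so the condition must be worded as drop-out with nothing recovered. The analysed rates are unaffected.

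The planned test is an exact stratified CMH test, so neither 92% nor 86–87% is its power. As a rough check only, an unstratified Fisher test at 0.05 without an interim look gives 90.0% with no loss and 83.4% at u = 5%. The documents give no stratum mix or stratum effects from which to compute the planned test's power. This is a good reason not to print about 92% as the power with complete data.

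Finally, the SAP labels the calculation as original, cancels the interim analysis and reports stopping at about 26% of enrolment. That limits the weight of the point. It does not remove it, because the SAP still carries both the power statement and the failure rule without reconciling them.

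**Conclusion.** The point holds conditionally and is minor. The approximate 90% describes a calculation with drop-outs removed or ignored. It does not describe the specified primary analysis at the plan's own 5% drop-out unless 90-day status is recovered for about half or more of the drop-outs. With none recovered, Normal-approximation power at 140 per arm is about 86–87%, so the chance of missing the target effect is about 13–14% rather than about 10%.

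This rests on equal drop-out in both arms, drop-out independent of VOC risk, and 35% and 17.5% as rates of VOCs actually experienced. The documents support the last for placebo (SAP 2.3.1) and do not address the first two. They give no expected recovery rate, so 86–87% should not be read as the trial's actual power. A reader might also infer that the sample size should have been larger or that the results are compromised. Neither follows: the final size was not set on statistical grounds, and no estimate, test or Type I error is affected.

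**What to change.** In SAP section 2.3, state how the 5% entered the original calculation, and add:

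> If 5% of participants per arm drop out, independent of VOC risk, and none has 90-day status recovered, so that all are counted as failures (38.25% vs 21.63%), 140 per arm gives about 86–87% power by the Normal approximation used for the original calculation; the planned exact stratified CMH test may give lower power.

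Repeat this in Protocol section 8.2 and the synopsis only if they are reissued. The cost is one recalculation and one or two sentences. No change of sample size is requested.
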